The safety and efficacy clinical validation to obtain the CE marking for the EmoLED device for the treatment of acute surgical wounds is ongoing. In particular, the acute observations, whose detailed results are provided in the attached final Report on the clinical trial, have once again demonstrated the device's safety and efficacy in shortening the healing time of spontaneously healing wounds. Isolated observations in patients with chronic lesions, of various aetiologies, have shown that the device is capable of unblocking the healing process, thus allowing the wound to progress beyond the inflammatory phase by inducing re-epithelialisation and wound closure. Observations made using a thermal camera have also shown that, due to the compromised condition of the tissues surrounding the ulcers, the baseline temperature of the limb is lower than normal and that both during and after treatment with the EmoLED device, the temperature never exceeds 40°C.

Information related to the clinical investigation

Study description

The commercial purpose of this study is to value the clinical efficacy of a battery-powered device that uses blue LEDs.

The study aims to compare the response of an existing standard treatment for second and third stage pressure sores, with a protocol that plans the administration of the EmoLED treatment three times a week for 4 consecutive weeks in addition to the conventional therapy.

Primary and secondary objectives

The primary objective of the study will be to assess the clinical efficacy of a treatment made through a battery-powered portable medical device that uses blue LEDs, in addition to the conventional therapy, applied on second and third degree pressure sores, compared to the conventional treatment alone, at the end of the fourth week of observation. As secondary objectives, the study proposes the clinical evaluation of lesions during the 4 weeks of treatment, and the evaluation of the treatment’s safety.

Endpoints

Primary endpoint of the study

The primary endpoint of the study is the assessment of the clinical state of second and third stage ulcers by reducing the index of the PUSH scale, in the two treatment groups at the end of the 4-week observation period.

Secondary endpoints

1. The assessment, during the weeks of observation, of the percentage of reduction of the lesion area compared to V0 in the second and third stage lesions in the two treatment groups;

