If the patient has two or more decubitus lesions at the same stage, the doctor will choose to treat the lesion of which, in his opinion, the data acquisition (photography and size measurement) is better. If a patient has two or more lesions of different stages, the doctor will decide to include in the study only one of them, based on the number of lesions inserted at that time in the two groups, choosing the group with a smaller number: In this way, attempts are made to ensure a numerical trend as simultaneous as possible in the two groups of lesions (e.g. if the number of 2°stage lesions enlisted is less than the number of 3°stage lesions enlisted, then the 2°stage lesion will be included in the study). In the case of a numerical parity of the two groups of lesions, the doctor will decide to treat the lesion with a position that allows a better data acquisition (photographic image, measurement, etc.).

Case Report Forms

Case Report Forms are unique to every patient. It will be used the form of injury assessment already present at the Investigator Centre; the data collection by the Principal Investigator includes: patient's name and surname, date of birth, room number, medical record number, date of surgery, any allergies and the characteristics of the lesion under investigation -position and degree of the lesion-. Another section dedicated to the characteristics of the lesion, includes: dimensions (length x width), the amount of exudate and the type of tissue. All these features will be evaluated, according to the criteria of the international scale PUSH, with a score, specified in the legend in the form, of which the total will be reported at each visit.

The Pressure Ulcer Scale for Healing (PUSH) is a tool designed by the National Pressure Ulcer

Advisory Panel (NPUAP) and used to observe the trend of pressure ulcers over time, classifying them regarding the area of extension, the exudate and the tissue type, noting the partial score for each characteristic of the ulcer and summing those scores to obtain the total. Comparing the relevant total scores over time will provide an indication of the improvement or worsening of the healing of the pressure ulcer.

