In addition, the data collected with the CRF, and other data from the medical records of patients enrolled, will be grouped and reported, in pseudonymized form, in a computerized database on three forms, generated with Forms of Microsoft, which will be filled by the health care personnel of the study team of the Experimental Center and which will be accessible to EMOLED staff of the Clinical Affairs Area. Specifically: in the Form "Patient Card", to be filled in during the enlistment phase, general clinical information is collected (alphanumeric ID associated with the enlisted patient, anamnesis, check of inclusion/exclusion criteria, Braden scale, etc.); in the Form "Patient Card Integration", also to be completed during the enlistment phase, are reported comorbidity, drug therapies and any allergies; while in the last Form "Patient Visit" the data relating to each of the three weekly visits provided for by the protocol are entered, namely those relating to the parameters of the PUSH scale (size of the lesion, exudate and type of tissue), the dressings and any notes.

The Braden scale, present in the Form "Patient Card", is used to assess the risk of the onset of pressure ulcers and, in particular for patients in prolonged stay or who are not able to move in total autonomy, is an assessment to be repeated at least once a week. The Braden scale takes into account 6 factors: sensory perception (ability to respond to discomfort dictated by compression), moisture of the skin (sweating, moisture linked to possible urinary and/ or fecal incontinence), motor activity (level of physical activity), mobility (ability to control/change the position of the body), nutrition (an adequate intake of calories, proteins, vitamins and minerals is essential to prevent the onset of new lesions) and, finally, friction and slipping (the friction force created with the solid surface and/or the linen can accelerate the onset of PU). Variables are ascribed to each factor and it is interpreted according to the principle that the lower the value resulting from the sum of all scores, the higher the risk of injury.

In the mentioned forms, the anonymity of patients will be guaranteed through the association of the patient's sensitive data with a progressive numerical ID. The register of this association will be accessible only to the medical staff of the structure that is part of the study team.

Photographic images acquisition

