Being diabetes a condition that affects the timing of wound healing, and being widely distributed in the population under study, enlisted patients will also be randomized for this factor, so that the two treatment groups can be homogeneous.

The randomization grid is generated with the on-line software available on the website "randomization.com".

The 2° stage and 3° stage lesions are randomized separately, as well as diabetic and non-diabetic patients.

It is a 1:1 randomization, stratified, with 4 blocks of 10 patients distributed in the two groups (treated and control).

Patient selection

All patients under treatment who meet all the inclusion criteria listed below will be considered for

inclusion in this study. Patients will be evaluated using a standard procedure that includes the collection of the medical history and a physical examination of the patient.

Inclusion Criteria

- Patients with 2° or 3° stage lower limb/ sacrum located pressure ulcers;
- Patients with 2° or 3° stage pressure ulcers with a $\geq 2\text{cm}^2$ lesion area;
- Patients with a hospitalization waiting time < 30 day;
- Men and women aged ≥ 50 years;
- Patients with a Braden scale score ≥ 11 ;

Exclusion criteria

- Patients who are participating in other clinical trials with drug or medical device;
- Patients with third stage pressure lesions, on the lower limbs or on the sacrum, with undermining wounds, tunneling or eschar;
- Patients with systemic or superficial infection at the time of recruitment, that need systemic antibiotic therapy;
- Patients with a history of self-harm who can voluntarily alter the course of healing;
- Patients under intravenous therapy with doses of corticosteroids above 40mg/day;
- Patients under immunosuppressant or cytostatic drugs therapy;
- Women who are pregnant or breastfeeding¹;
- Patients with neoplasia;
- Patients with pathologies that induce skin photosensitivity;
- Patients with a life expectancy of less than 30 days.

In order to be eligible for the planned treatment phase, all the inclusion and exclusion criteria must be met. Any concomitant pharmacological therapy must be maintained.

Number of patients expected to enroll

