Early termination and suspension of clinical evaluation

In the event of suspension or early termination of the study by the promoter, taken as a safety measure due to events related to the conduct of the study that may affect the health of the patients recruited, the promoter is required to notify the Ministry of Health and the Ethics Committees involved within 90 days from the recruitment of the last patient or the early closure. In case of suspension or early termination of the study not for safety reasons, the sponsor shall justify and explain their decision. The suspended clinical trial cannot be reactivated unless a substantive amendment and the positive opinion of the Ministry of Health and the Ethics Committees have been submitted.

Statistics

Calculation of the sample number

Lack of reliable data in the scientific literature on average recovery times of decubitus ulcers (PUs), the absence of clinical experience combining blue light treatments with the therapy of this type of lesion, and the lack of reliability about any inference based on clinical studies that associate this type of treatment with other types of skin lesions, due to the different aetiologies and types of patients, do not make possible to perform a reliable calculation of the sample number. The predefined sample size was therefore set on the basis of considerations concerning the recruitment capacity of the centre involved in the project. Based on an estimate of the historical clinical activity data at the Cardiorespiratory Rehabilitation Units, at the Neuro-Motor Rehabilitation Unit and at the Acquired Severe Brain Injury Unit (UGCA), where patients will be enrolled, the percentage of patients with decubitus ulcers at the entrance is about 20%, an information that implies that compared to an average of about 426 patients/ year, in 10 months of enrollment it is possible to reach a number of 40 patients compared to a percentage of drop-out/ waste equal to about 25%. A total of 40 patients will be recruited, 20 patients with second stage PUs and 20 patients with third stage PUs. Thus, this study is intended as a "proof of concept", the results of which may be used as preliminary information to define the sample size in later studies.

Management of missing data

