Since it is a "proof of concept" study based on a limited number of patients, we will include in the study also patients who do not conclude the study according to the principle "intention to treat" and the resulting missing data will be processed through the imputation technique of the missing data *last observation carried forward - LOCF*. If the patient does not leave the study but skips one or more visits, the averages of the two adjacent visits or the last available data (LOCF) will be taken into account.

Statistical analysis

Demographic and clinical data will be presented in tables and graphs in the form of frequencies and percentages for categorical variables, mean, standard deviation, median and interquartile range for continuous variables, differentiating by reference population and treatment group. At a first analysis a qualitative comparison will be carried out between the treatment groups (improvement or not improvement), both general and differentiated for lesion of 2° and 3° stage, through the χ^2 test or Fisher's exact test for counts of less than 5. The results will be presented in contingency tables and bar charts.

A quantitative comparative statistic between the treatment groups will then be performed by comparing the outcome variables (percentage reduction of the lesion area and reduction of the PUSH index) through the non parametric test of Mann-Whitney, one of the most powerful nonparametric tests used to verify whether two independent groups belong to the same population. The Mann-Whitney test is usually applied when the assumptions to perform the parametric test are not met, which means when the distribution of the variable under study is not normal and/or the sample sizes are reduced (n 30 cases in at least one sample).

In this case, the choice to perform a non parametric analysis lies in the low sample size and therefore it is preferred to have more conservative meaningfulness values. The results will be presented in tables, with median and interquartile interval in the two groups with the relative p. value, and graphically, through box plot.

To analyse the internal and between groups time-related differences, Friedman's non-parametric test for the outcome variables will be performed.

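### The PUSH comparison ignores the randomisation strata and baseline, no analysis is named primary, and the adjusting model leaves both strata unnamed

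*Combined protocol and SAP*

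**What the plan says.** All places are in the combined protocol and SAP.

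- **Primary endpoint of the study.** The clinical state of the ulcers is assessed "by reducing the index of the PUSH scale, in the two treatment groups at the end of the 4-week observation period".
- **Bias.** Allocation is 1:1 and stratified: "The 2° stage and 3° stage lesions are randomized separately, as well as diabetic and non-diabetic patients". The reason given for the second factor is "Being diabetes a condition that affects the timing of wound healing".
- **Case Report Forms.** The form carries the "position and degree of the lesion" and the PUSH items, "of which the total will be reported at each visit". On an enrolment form "are reported comorbidity, drug therapies and any allergies".
- **Statistical analysis.** Four analyses are listed: improved versus not improved by chi-square or Fisher, overall and by stage; "reduction of the PUSH index) through the non parametric test of Mann-Whitney", with percentage area reduction tested the same way; Friedman's test over time; and GLMs with demographic and clinical covariates and the pre-treatment measurement. None is called primary, and one 0.05 threshold covers every test. For the Mann-Whitney the planned output is group medians, interquartile intervals and a p-value.
- **Calculation of the sample number.** The 40 patients come from recruitment capacity. The study is a proof of concept whose results "may be used as preliminary information to define the sample size in later studies".

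**The concern.** Stratified randomisation balances the arms on stage and diabetes. A test that ignores those factors still counts their variation as noise. If they predict the change in PUSH, its true size falls below 5% and power is lost. Leaving out baseline PUSH also loses power if baseline predicts the reduction; subtracting baseline to form a change score is not the same as adjusting for it.

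A separate matter is that four kinds of analysis share one threshold and none has precedence. If the Mann-Whitney and the GLM disagree, nothing says which result answers the primary question. The GLM's covariates, family and link are also left open.

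Third, a study meant to inform later sample sizes should deliver a group difference in PUSH points with its uncertainty. Two medians and a p-value do not supply that.

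**Working it through.** **The plan's own figure.** No power calculation exists to reproduce. The recruitment inputs give 426 × 10/12 × 0.20 = 71 patients with ulcers, and 71 × 0.75 = 53 after 25% loss. That covers 40 but does not derive it. There are 10 per arm in each stage, so 20 per arm overall.

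**What 20 per arm can detect** (two-sided 0.05, 80% power): (1.960 + 0.842) × √(2/20) = 0.89 SD. Allowing for Mann-Whitney efficiency of 3/π under normality, it is 0.91 SD. An effect of 0.9 SD is therefore used below.

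**Reading the text.** The split by stage belongs to the improved/not-improved comparison, and the split by reference population belongs to the descriptive tables. Neither attaches to the Mann-Whitney.

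**Simulation.** There were 20,000 trials per scenario (Monte Carlo SE at most 0.35 points). Each trial had four stage-by-diabetes strata of 10, 5 per arm. The documents give no SDs or stratum effects, so every input is assumed. The within-stratum SD is 1:

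reduction = s·stage + d·diabetes + ρ·baseline + √(1−ρ²)·error + 0.9·arm

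Tests compared:
- Mann-Whitney with tie and continuity correction.
- Rank ANCOVA: rank(reduction) regressed on arm, stage, diabetes and rank(baseline), with a t test on arm (40 − 5 = 35 df).

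Power (%), Mann-Whitney vs rank ANCOVA:

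| Stage shift s | Diabetes shift d | ρ | Normal errors | t errors, 5 df |
|---|---|---|---|---|
| 0 | 0 | 0 | 77 vs 76 | 85 vs 84 |
| 0 | 0.3 | 0 | 76 vs 76 | 85 vs 85 |
| 0 | 0.3 | 0.3 | 76 vs 79 | 83 vs 86 |
| 0.5 | 0.3 | 0.3 | 74 vs 79 | 80 vs 86 |
| 1 | 0.3 | 0 | 67 vs 75 | 74 vs 82 |
| 1 | 0.3 | 0.3 | 67 vs 79 | 73 vs 84 |

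Rank ANCOVA minus Mann-Whitney, in points, for normal / t5 / t3 / log-normal errors:
- nothing prognostic: −1.1 / −0.8 / −0.4 / −0.3
- diabetes only: −0.3 / −0.2 / −0.1 / 0.0
- last row of the table: +11.2 / +10.9 / +10.3 / +8.8

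Rounding to integer scores (assumed SD 3 points, normal errors) moves either test by at most 0.5 points.

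**Size at nominal 5%.** The Mann-Whitney falls to 3.0-4.3% at a 0.5 SD stage shift and 1.3-2.6% at 1 SD. Rank ANCOVA stays at 4.8-5.6%.

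**Ordinary ANCOVA as the test.** With nothing prognostic its power against the Mann-Whitney is 78 vs 77 (normal), 79 vs 85 (t5), 83 vs 95 (t3) and 81 vs 97 (log-normal). It is a poor choice for the primary test. Its 95% CI still covers 94.8-95.9% in all four shapes, with a width of 1.15-1.29 SD, so it can serve as the estimate.

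**Open choice, no treatment effect.** Improvement is assumed to mean a reduction above 0. At least one of Mann-Whitney and adjusted GLM reaches p<0.05 in 5.5-6.7% of trials. Adding the improved/not-improved test gives 6.3-7.9%. Friedman and free choice of covariates are not counted, so this is not an upper bound.

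**The case against.** The strongest reply is that adjustment is already planned: the GLM includes the pre-treatment measurement, and stage and diabetes are clinical variables. That is right for baseline. For the strata it shows that adjustment is possible, not that it is specified, and it gives the GLM no precedence.

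Second, the only prognostic factor the protocol asserts is diabetes, with no size given, and in the diabetes-only row the gain is nil. The larger gains need an assumed stage effect or baseline correlation. This stands.

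Third, the study is a proof of concept with no power target, and the plan says it prefers conservative p-values. That lowers the weight of the point. The stated reason, small samples, supports a rank-based test; it does not explain leaving out the design factors.

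Fourth, the structure narrows the choice: one primary endpoint, one test named for the quantitative comparison, and the others given different purposes. The error inflation computed is modest. Still, no analysis is designated primary. The descriptive tables may also give means and SDs by arm, if they extend to outcomes, from which an unadjusted interval could be derived.

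Finally, other remedies are valid, such as a van Elteren test by stage and diabetes, though that does not use baseline. Pairing a rank test with a Gaussian interval has a cost too: with a 0.9 SD effect the two disagree on significance in about 5-17% of simulated trials, depending on error shape. The plan must therefore say that the rank ANCOVA decides and the interval estimates.

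**Conclusion.** The concern holds; it is a change that should be made, not a flaw that invalidates the trial. The missing primary analysis, the unnamed strata and the missing interval are plain on the text and depend on no simulation. The efficiency loss depends on assumptions: none if diabetes alone matters at 0.3 SD, about 5 points at a 0.5 SD stage shift with baseline correlation 0.3, and about 11 at 1 SD. Against that, the adjusted rank test loses at most 1.1 points if nothing is prognostic. The simulations assume 10 patients in each stage-by-diabetes cell, whereas the section on patient numbers fixes only the totals per stage.

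**What to change.** 1. Designate one primary analysis of week-4 PUSH reduction: rank ANCOVA on arm, stage, diabetes and ranked baseline PUSH. This keeps the plan's rank-based approach.
2. In the GLM, name stage, diabetes and baseline PUSH, and state the family and link (Gaussian, identity). Report the adjusted mean difference in PUSH points with a 95% CI as the estimate for later sample sizes. State that the rank ANCOVA governs the test.
3. Label the plain Mann-Whitney, the improved/not-improved comparison and Friedman's test as supportive. Do not make ordinary ANCOVA the primary test.

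No extra patients or data are needed. The cost is 0.3-1.1 points of power if nothing is prognostic, plus the administrative step. Under the sections on plan deviations and amendments, the change may need Ethics Committee approval, and a substantive amendment suspends the trial until it is approved. It is best made before enrolment or together with another amendment, and in any case before the data are analysed.

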2. Safety of treatment (number of related adverse events in the two groups).

Measurable parameters

After enrolment and signature of the informed consent, the salient data, in the appropriate case report form, and the photographic images of the 2° and 3° stage injuries of each patient will be collected.

Three times a week (in conjunction with the dressing change) data, on patient forms, will be recorded, while once a week and at the last visit, if healing has not occurred before, the photographic images of each lesion of 2° and 3° stage will be captured.

All these variables will be measured during the 4-week observation period. The date of recovery, if it occurs before the end of the observation period, will be recorded in the patient’s case report form and the photographic image of the healed area will be acquired.

WEEK	W 1			W 2			W 3			W 4		
VISIT	V 1	V 2	V 3	V 4	V 5	V 6	V 7	V 8	V 9	V 10	V 11	V 12
CRF	P	P	P	P	P	P	P	P	P	P	P	P
PICTURE	P			P			P			P		P

Recording of clinical data

Data related to the evaluation of the endpoints are acquired during the visit for both study groups and will be inserted in pseudonymized form within a computerized database, where each subject will be associated with an alphanumeric identification code. The key of patient association code will be kept by the Principal Investigator for the duration of the study, it will not be communicated to the Sponsor and to the scientific coordinator and it will be eliminated at the end of the study, making the data completely anonymous.

The parameters of the Case Report Form and the photographic images of the lesions are both acquired and stored in digital format, during the length of the clinical trial and afterwards, for 10 years after the conclusion of the study.

Once the storage period indicated above has expired, the data will be anonymized so that it is no longer possible to trace, directly or indirectly, the identity of the interested subject. Anonymized data may be reused for further research and may therefore be stored indefinitely.

Each photograph of the lesions will be identified only with the patient code and the date of the visit.

The analysis of the photographic images will be performed through an appropriate analysis algorithm that measures in mm² the surface of the lesion.

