Generalized linear models (GLM) will be used to investigate whether differences between the two groups are influenced in a confounding way by demographic and clinical covariates, pre-treatment measurement, and to measure their impact that will allow us to understand which variables affect the outcome and will also allow us to analyse the differences between groups being equal for these covariates.

A descriptive statistic of adverse events, if present, will also be made through tables with frequencies and percentages, and bar charts.

All significance tests will have a statistically significant p. value <0.05. The analysis will be carried out with the open source software R Commander (v. 2.2-0).

croData publication policy

At the end of the clinical study and of the related analysis about the obtained results, these will be made available anonymously and aggregated in full respect of the protection of the right to privacy, in accordance with Regulation no. 2016/679 (GDPR, General Data Protection Regulation), for publication in national or international journals, or for presentation by investigators at scientific conferences and in medical journals. For the writing of any publications concerning the study in question, may be used professional medical writers who will write manuscripts on behalf of the company and for which the company undertakes to ensure analogous compliance with current legislation.

After the conclusion of the study, the sponsor will be responsible for drawing up the final report of the clinical trial in the manner and timing prescribed in the current legislation regarding clinical investigations; external consultants of the sponsor, experts in this field, may be involved in the preparation of the final report and for which the sponsor ensure the same compliance with current legislation.

References

1. Clark R (1985) Cutaneous tissue repair: basic biological considerations. *J Am Acad Dermatol* 13: 701-725.
3. Nwomeh BCM Yager DR, Cohen IK (1998) Physiology of the chronic wound. *Clinics in Plastic Surgery* 25 (3): 341
4. Hackam DJ, Ford HR (2002) Cellular, biochemical and clinical aspects of wound healing. *Surgical Infections* 3: S23-S35.
5. Calderhead (2007), The photobiological basis behind light-emitting diode (LED) phototherapy, *Laser therapy*.

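### Friedman's test cannot compare the two arms over time, and the plan specifies no other analysis of the between-arm time course for lesion area or PUSH.

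*Combined protocol and SAP*

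**What the plan says.** The Statistical analysis section names four between-arm methods:

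- Chi-square or Fisher's exact test on improved versus not improved.
- Mann-Whitney: "comparing the outcome variables (percentage reduction of the lesion area and reduction of the PUSH index) through the non parametric test of Mann-Whitney". No visit is named.
- Friedman: "To analyse the internal and between groups time-related differences", with the further wording "non-parametric test for the outcome variables will be performed". The outcome variables are the two just listed.
- A generalized linear model for demographic and clinical covariates and the pre-treatment value, which "will also allow us to analyse the differences between groups being equal for these covariates". No visit, arm-by-time term or within-patient correlation is mentioned.

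The plan does pose a question over time. Secondary endpoint 1 is "The assessment, during the weeks of observation, of the percentage of reduction of the lesion area compared to V0", in the two treatment groups. Under Primary and secondary objectives, "the study proposes the clinical evaluation of lesions during the 4 weeks of treatment". The data are repeated measures. Area comes from photographs taken "once a week and at the last visit, if healing has not occurred before, the photographic images of each lesion", which the table under Measurable parameters places at V1, V4, V7, V10 and V12. PUSH is scored on a form "of which the total will be reported at each visit", at 12 visits.

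Allocation is 1:1 to parallel groups (Bias), with 20 patients per arm, 10 in each ulcer stage (Number of patients expected to enroll). The primary endpoint is PUSH reduction at the end of week 4.

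**The concern.** Friedman's test compares related measurements within blocks. Here arm is a between-patient factor, so the test fits the within-arm half of the sentence and not the between-arm half.

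It could be run in three ways, and none is a valid between-arm test over time:

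1. **Patients as blocks, visits as columns, arms pooled.** Arm does not enter the statistic. A significant result can come from healing that is the same in both arms.
2. **The same, separately in each arm.** This gives two tests of time and no comparison between them.
3. **Visits as blocks, arms as columns.** Arm does enter, but the visits come from the same patients, so the blocks are not independent.

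Secondary endpoint 1 would then be reported either with a p-value that says nothing about the device or with one that overstates the arm difference. A pooled result under a between-groups label could be read as a device effect when both arms simply healed.

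**Working it through.** **Inputs from the document.** 20 patients per arm, 40 in total; five photographs for area; 12 PUSH scores; significance at p < 0.05. The text does not say whether V0 is V1 or a separate measurement, so four and six area measurements are also shown. The document gives no standard deviation, slope or within-patient correlation, and no power calculation to reproduce. Every such value below is an assumption.

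**1. Patients as blocks.** For n patients and k visits with rank sums R_j, the statistic is 12/[nk(k+1)] × ΣR_j² − 3n(k+1). If every patient changes steadily in one direction, R_j = nj and ΣR_j² = n²k(k+1)(2k+1)/6. The statistic becomes 2n(2k+1) − 3n(k+1) = n(k−1). The size of the change has dropped out:

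| Visits k | Per arm, n = 20 | Pooled, n = 40 |
|---|---|---|
| 4 | 60.0 | 120.0 |
| 5 | 80.0 | 160.0 |
| 6 | 100.0 | 200.0 |
| 12 | 220.0 | 440.0 |

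Numerical runs with total declines of 10 and of 90 units return these same values. In a separate noisy data set, the pooled statistic was 91.8 as generated, 91.8 after moving the whole treated arm by 1000 points, and 91.8 after permuting the arm labels. Using percentage reduction instead of area changes nothing, because within a patient it only reverses the ranks.

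The pooled test detects healing. Take identical arms with assumed SDs of 20 between and 10 within patients. It is significant in 5% of trials with no healing, 75% at 2 units per week and 100% at 5 units per week. In the same runs, Mann-Whitney on each patient's slope rejects in 4.7% to 5.6%. The failure also runs the other way. With opposite trends of −2 and +2 points (assumed SDs 2 between patients, 1 residual, 1 for slope), pooled Friedman rejects in 0.6% of trials and Mann-Whitney on end change in 100%.

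**2. Separately by arm.** Under that second set of SDs, with identical arms and five visits, one arm is significant and the other not in up to 47% of trials (20 per arm, both falling 1 point). Reading that contrast as an arm difference would be an error.

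**3. Visits as blocks.** With two columns and m blocks, Q = (a − b)²/m, where a and b count the visits favouring each arm. If all five favour one arm, Q = 25/5 = 5 and p = 0.025. If the split is 4 to 1, Q = 9/5 = 1.8, which is not significant. With independent blocks the level at m = 5 would be 2 × (1/2)⁵ = 6.25%; at m = 4 it is 12.5% and at m = 12 it is 3.9%. With identical arms, 20 per arm and equal correlation between visits, simulated false-positive rates are:

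| Assumed correlation | 0 | 0.2 | 0.5 | 0.8 | 0.95 |
|---|---|---|---|---|---|
| 5 visits, arm medians | 6% | 12% | 24% | 43% | 64% |
| 5 visits, arm means | 6% | 15% | 33% | 59% | 79% |
| 12 visits, arm medians | 4% | 15% | 35% | 57% | 74% |

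These rates treat the correlation as that of the analysed values. If the analysed value is absolute change from a shared baseline, the equal-correlation model fixes the correlation between changes at 0.5. The covariance is σ²(1−ρ) and the variance 2σ²(1−ρ). Rates for arm medians are then 24% at five visits and 35% at 12 with a separate V0, and 31% at four visits if V1 is the baseline. For arm means there is an exact check: all m changes favour one arm when the baseline arm difference is the smallest or largest of m + 1, with probability 2/(m+1). At m = 5 that is 2/6 = 33%, matching the table.

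**The case against.** The strongest reply is that the gap is narrower than it looks. Secondary endpoint 1 is already a baseline-referenced percentage, and Mann-Whitney is named for that variable between arms. Run at each weekly photograph, it gives a valid comparison at each visit. The document states no arm-by-time objective. All of this is true of single visits. But the plan does not say that the test will be run weekly, separate weekly tests do not test whether the courses differ, and they raise a multiplicity question that is not addressed.

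Second, the visits-as-blocks arrangement is not proposed anywhere in the plan, and for a change-from-baseline outcome the full correlation range is too wide under the equal-correlation model. This stands in part. The change-based rates of 24% to 35% are the more relevant ones for arm medians under that model. They are still well above 5%, and the fixed correlation of 0.5 holds only under that model. The arrangement matters because it is the only one of the three in which arm enters at all.

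Third, the PUSH values of 220 and 440 need every score to fall at all 12 visits. Whole-point scores, early healing and carried-forward values will produce ties. Correct, so those values illustrate the formula and do not predict a result; ties do not bring arm into the statistic.

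Fourth, PUSH is defined as an endpoint only at week 4, so support for a PUSH time course is thinner. That is fair. It rests on the Friedman sentence covering both outcome variables and on the general secondary objective.

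Fifth, the plan never labels Mann-Whitney as the primary test. Also correct. What can be said is that the week-4 PUSH comparison does not depend on Friedman.

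**Conclusion.** The concern holds. As written, the only test named for between-group differences over time either carries no arm information or, with visits as blocks, rejects too often. The first result is exact and needs no assumed variance. The size of the inflation depends on an unknown correlation: 6% to 64% over correlations of 0 to 0.95 at five visits (arm medians), and 24% to 35% for absolute change from baseline under equal correlation. No other method in the plan is specified so as to fill the gap.

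The consequence is modest. It falls on secondary endpoint 1 and the secondary objective over the four weeks, in a 40-patient proof-of-concept study. The week-4 PUSH comparison is untouched by this point, which says nothing about other aspects of that comparison. Later sample sizes would draw on the reported medians and intervals more than on Friedman p-values. It should be corrected before analysis.

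**What to change.** In the Statistical analysis section:

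- Remove between-group differences from the Friedman sentence. Keep Friedman for within-arm description, and state that within-arm p-values will not be compared between arms.
- Name one between-arm analysis of the time course that includes arm, visit and arm-by-visit and allows for repeated measures, such as a rank-based longitudinal factorial analysis. A simpler acceptable choice is Mann-Whitney on one summary per patient, such as the slope. With 20 per arm, five visits and the second set of assumed SDs, it rejects in 5.4% of trials when both arms fall 2 points and in 96% when they fall 1 and 3 points.
- Apply it to area at the photograph visits and to PUSH at its scheduled visits, reported as secondary and descriptive. Say whether V0 is V1 or a separate measurement.
- State the visit for each Mann-Whitney test, and designate Mann-Whitney on PUSH reduction at the end of week 4 as the primary comparison.

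The cost is one paragraph of statistical text and a little more analysis work. No new data, visits or patients are needed.
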